**Table 4: Distribution of Protocol Deviations by Category, Type and Study Group**

Category	Deviation Type	All (N = 120)	COVIVAC				Placebo (N = 20)
		n (%)	1 µg (N = 25)	3 µg (N = 25)	10 µg (N = 25)	1 µg + CpG (N = 25)	
Eligibility/enrollment	Any type	xx (xx.x%)	xx (xx.x%)	xx (xx.x%)	xx (xx.x%)	xx (xx.x%)	xx (xx.x%)
	Did not meet inclusion/exclusion criteria but enrolled						
	Informed consent not taken						
	Incorrect informed consent process						
	Other						
Vaccination procedure	Any type						
	Randomized to wrong treatment arm: Dosed with wrong treatment arm at V1						
	Wrong treatment arm administered at 2 nd dose						
	Dosed when withdrawal/discontinuation criteria were met						
	Incorrect vaccination procedure						
	Damaged/ expired IP/ quarantined kit used without prior approval						
	Other						
Missed procedures	Any type						
	Pre-vaccination blood sample missed to be collected from eligible subject but subject continued in the study						
	Post-vaccination blood sample missed to be collected from eligible subject						
	Assessments at scheduled visits were not performed						
	Post-vaccination assessment missed						
	DC/thermometer and/or ruler not provided to subject after vaccination						
	Other						

**Table 4: Distribution of Protocol Deviations by Category, Type and Study Group (continued)**

Category	Deviation Type	All (N = 120)	COVIVAC				Placebo (N = 20)
			1 µg (N = 25)	3 µg (N = 25)	10 µg (N = 25)	1 µg + CpG (N = 25)	
		n (%)	n (%)	n (%)	n (%)	n (%)	n (%)
Visit window	Any type						
	Out of window visit						
	Missed visit/ visit not conducted						
	Missed vaccine administration						
	Delayed vaccine administration						
	Other						
etc.	etc.						

**Note:** Number of subjects in the safety analysis population

**Table 5: Subject Disposition by Study Group**

Status	All (N = 120)	COVIVAC				Placebo (N = 20)
		1 µg (N = 25)	3 µg (N = 25)	10 µg (N = 25)	1 µg + CpG (N = 25)	
	n (%)	n (%)	n (%)	n (%)	n (%)	n (%)
Screened	xxx	NA	NA	NA	NA	NA
Not eligible	xxx					
Eligible	xxx					
Not randomized	xxx					
[Reason 1]	xxx					
[Reason 2]	xxx					
[etc.]	xxx					
Randomized	xxx					
Received 1st dose vaccination	xx (xx.x%)	xx (xx.x%)	xx (xx.x%)	xx (xx.x%)	xx (xx.x%)	xx (xx.x%)
Received 2nd dose vaccination	xx (xx.x%)	xx (xx.x%)	xx (xx.x%)	xx (xx.x%)	xx (xx.x%)	xx (xx.x%)
[Reason 1]						
[etc.]						
Completed Day 29 visit						
Completed Day 57 visit						
Completed the study						
Not completing the study						
Reason for not completing the study						
- Serious adverse event						
- Non-serious adverse event						
- Protocol deviation						
- Consent withdrawal						

**Table 5: Subject Disposition by Study Group (continued)**

Status	All (N = 120)	COVIVAC				Placebo (N = 20)
	n (%)	1 µg (N = 25)	3 µg (N = 25)	10 µg (N = 25)	1 µg + CpG (N = 25)	
- Migrated / Moved from the study area						
- Lost to follow-up						
- Other reason						

**Safety analysis population**

**Full analysis population**

**Per protocol population**

**Note:** + CpG1018 1.5 mg (Adjuvant)

“xx” represent the value number.

“xx.x %” is the percentage calculated from total number of 1st dose vaccinated subjects (N).

**Table 6: Summary of Screen Failures**

Inclusion/Exclusion Category	Inclusion/Exclusion Criterion	n a	% b
Inclusion and Exclusion	Number of subjects failing any eligibility criterion	xx	xx.xx
Inclusion	Any inclusion criteria		
	[inclusion criteria 1]		
	[inclusion criteria 2]		
	[inclusion criteria 3]		
	.....		
Exclusion	Any exclusion criteria		
	[exclusion criteria 1]		
	[exclusion criteria 2]		
	[exclusion criteria 3]		
	.....		

a More than one criteria may be marked per subject.

b Denominator for percentages is the total number of screen failures.

**Note:** Include all inclusion and exclusion criteria listed in the protocol.

**Table 7: Analysis Populations by Study Group and Visit**

Visit	Reason subjects excluded	All (N = 120)	COVIVAC				Placebo (N = 20)
			1 µg (N = 20)	3 µg (N = 20)	10 µg (N = 20)	1 µg + CpG (N = 20)	
Total							
vaccinated							
	Number vaccinated						
	Number not vaccinated						
	[Reason 1]						
	[Reason 2]						
	[etc.]						
Per protocol							
Population							
	Included						
	Excluded						
	[Reason excluded]						
	[etc.]						
28 days after the first vaccination (D29)							
	Included						
	Excluded						
	[Reason excluded]						
	[etc.]						
14 days after the second vaccination (D43)							
	Included						
	Excluded						
	[Reason excluded]						
	[etc.]						
6 months after the second vaccination (D197)							
	Included						
	Excluded						
	[Reason excluded]						
	[etc.]						
12 months after the second vaccination (D365)							
	Included						
	Excluded						
	[Reason excluded]						
	[etc.]						
etc.							

N = Number of participant in Enrolled population.

 Denominator for percentage is N.  Denominator for percentage is number vaccinated. Reasons for exclusion do not missing data, which is specific to each parameter.

**Table 8: Summary of Categorical General Characteristics at Screening, Exposed Population**

Characteristics	All (N=120)	COVIVAC				Placebo (N = 20)
		1 µg (N = 25)	3 µg (N = 25)	10 µg (N = 25)	1 µg + CpG (N = 25)	
Sex, n (%)						
Male	xx (xx.x%)	xx (xx.x%)	xx (xx.x%)	xx (xx.x%)	xx (xx.x%)	xx (xx.x%)
Female	xx (xx.x%)	xx (xx.x%)	xx (xx.x%)	xx (xx.x%)	xx (xx.x%)	xx (xx.x%)
Race, n (%)						
Asian	xx (xx.x%)	xx (xx.x%)	xx (xx.x%)	xx (xx.x%)	xx (xx.x%)	xx (xx.x%)
Other	xx (xx.x%)	xx (xx.x%)	xx (xx.x%)	xx (xx.x%)	xx (xx.x%)	xx (xx.x%)
Ethnicity, n (%)						
Kinh	xx (xx.x%)	xx (xx.x%)	xx (xx.x%)	xx (xx.x%)	xx (xx.x%)	xx (xx.x%)
Other	xx (xx.x%)	xx (xx.x%)	xx (xx.x%)	xx (xx.x%)	xx (xx.x%)	xx (xx.x%)

**Note:** + CpG1018 1.5 mg (Adjuvant)

“xx” represent the value number.

**Table 9: Summary of Categorical General Characteristics at Screening, Per Protocol Population**

Characteristics	All (N=120)	COVIVAC				Placebo (N = 20)
		1 µg (N = 25)	3 µg (N = 25)	10 µg (N = 25)	1 µg + CpG (N = 25)	
Sex, n (%)						
Male	xx (xx.x%)	xx (xx.x%)	xx (xx.x%)	xx (xx.x%)	xx (xx.x%)	xx (xx.x%)
Female	xx (xx.x%)	xx (xx.x%)	xx (xx.x%)	xx (xx.x%)	xx (xx.x%)	xx (xx.x%)
Race, n (%)						
Asian	xx (xx.x%)	xx (xx.x%)	xx (xx.x%)	xx (xx.x%)	xx (xx.x%)	xx (xx.x%)
Other	xx (xx.x%)	xx (xx.x%)	xx (xx.x%)	xx (xx.x%)	xx (xx.x%)	xx (xx.x%)
Ethnicity, n (%)						
Kinh	xx (xx.x%)	xx (xx.x%)	xx (xx.x%)	xx (xx.x%)	xx (xx.x%)	xx (xx.x%)
Other	xx (xx.x%)	xx (xx.x%)	xx (xx.x%)	xx (xx.x%)	xx (xx.x%)	xx (xx.x%)

**Note:** + CpG1018 1.5 mg (Adjuvant)

“xx” represent the value number.

**Table 10: Summary of Continuous General Characteristics at Screening, Exposed Population**

	All (N=120)	COVIVAC				Placebo (N = 20)
		1 µg (N = 25)	3 µg (N = 25)	10 µg (N = 25)	1 µg + CpG (N = 25)	
Age (years)						
n	xx	xx	xx	xx	xx	xx
Mean (SD)	xx.xx (xx.xx)	xx.xx (xx.xx)	xx.xx (xx.xx)	xx.xx (xx.xx)	xx.xx (xx.xx)	xx.xx (xx.xx)
Median (q1-q3)	xx (xx-xx)	xx (xx-xx)	xx (xx-xx)	xx (xx-xx)	xx (xx-xx)	xx (xx-xx)
Min-Max	xx-xx	xx-xx	xx-xx	xx-xx	xx-xx	xx-xx
Weight (kg)						
n	xx	xx	xx	xx	xx	xx
Mean (SD)	xx.xx (xx.xx)	xx.xx (xx.xx)	xx.xx (xx.xx)	xx.xx (xx.xx)	xx.xx (xx.xx)	xx.xx (xx.xx)
Median (q1-q3)	xx (xx-xx)	xx (xx-xx)	xx (xx-xx)	xx (xx-xx)	xx (xx-xx)	xx (xx-xx)
Min-Max	xx-xx	xx-xx	xx-xx	xx-xx	xx-xx	xx-xx
Height (cm)						
n	xx	xx	xx	xx	xx	xx
Mean (SD)	xx.xx (xx.xx)	xx.xx (xx.xx)	xx.xx (xx.xx)	xx.xx (xx.xx)	xx.xx (xx.xx)	xx.xx (xx.xx)
Median (q1-q3)	xx (xx-xx)	xx (xx-xx)	xx (xx-xx)	xx (xx-xx)	xx (xx-xx)	xx (xx-xx)
Min-Max	xx-xx	xx-xx	xx-xx	xx-xx	xx-xx	xx-xx
BMI (kg/m^2)						
n	xx	xx	xx	xx	xx	xx
Mean (SD)	xx.xx (xx.xx)	xx.xx (xx.xx)	xx.xx (xx.xx)	xx.xx (xx.xx)	xx.xx (xx.xx)	xx.xx (xx.xx)
Median (q1-q3)	xx (xx-xx)	xx (xx-xx)	xx (xx-xx)	xx (xx-xx)	xx (xx-xx)	xx (xx-xx)
Min-Max	xx-xx	xx-xx	xx-xx	xx-xx	xx-xx	xx-xx

**Note:** + CpG1018 1.5 mg (Adjuvant)

“xx” represent the value number.

**Table 11: Summary of Continuous General Characteristics at Screening, Per Protocol Population**

	All (N=120)	COVIVAC				Placebo (N = 20)
		1 µg (N = 25)	3 µg (N = 25)	10 µg (N = 25)	1 µg + CpG (N = 25)	
Age (years)						
n	xx	xx	xx	xx	xx	xx
Mean (SD)	xx.xx (xx.xx)	xx.xx (xx.xx)	xx.xx (xx.xx)	xx.xx (xx.xx)	xx.xx (xx.xx)	xx.xx (xx.xx)
Median (q1-q3)	xx (xx-xx)	xx (xx-xx)	xx (xx-xx)	xx (xx-xx)	xx (xx-xx)	xx (xx-xx)
Min-Max	xx-xx	xx-xx	xx-xx	xx-xx	xx-xx	xx-xx
Weight (kg)						
n	xx	xx	xx	xx	xx	xx
Mean (SD)	xx.xx (xx.xx)	xx.xx (xx.xx)	xx.xx (xx.xx)	xx.xx (xx.xx)	xx.xx (xx.xx)	xx.xx (xx.xx)
Median (q1-q3)	xx (xx-xx)	xx (xx-xx)	xx (xx-xx)	xx (xx-xx)	xx (xx-xx)	xx (xx-xx)
Min-Max	xx-xx	xx-xx	xx-xx	xx-xx	xx-xx	xx-xx
Height (cm)						
n	xx	xx	xx	xx	xx	xx
Mean (SD)	xx.xx (xx.xx)	xx.xx (xx.xx)	xx.xx (xx.xx)	xx.xx (xx.xx)	xx.xx (xx.xx)	xx.xx (xx.xx)
Median (q1-q3)	xx (xx-xx)	xx (xx-xx)	xx (xx-xx)	xx (xx-xx)	xx (xx-xx)	xx (xx-xx)
Min-Max	xx-xx	xx-xx	xx-xx	xx-xx	xx-xx	xx-xx
BMI (kg/m^2)						
n	xx	xx	xx	xx	xx	xx
Mean (SD)	xx.xx (xx.xx)	xx.xx (xx.xx)	xx.xx (xx.xx)	xx.xx (xx.xx)	xx.xx (xx.xx)	xx.xx (xx.xx)
Median (q1-q3)	xx (xx-xx)	xx (xx-xx)	xx (xx-xx)	xx (xx-xx)	xx (xx-xx)	xx (xx-xx)
Min-Max	xx-xx	xx-xx	xx-xx	xx-xx	xx-xx	xx-xx

**Note:** + CpG1018 1.5 mg (Adjuvant)

“xx” represent the value number.

**Table 12: Overall Events of Medical History by System Organ Class (SOC) and Preferred Term (PT)**

System Organ Class (SOC)	Preferred Term (PT)	All (NE = xx)	COVIVAC				Placebo (NE = xx)
			1 µg (NE = xx)	3 µg (NE = xx)	10 µg (NE = xx)	1 µg + CpG (NE = xx)	
All SOC	All PT	xx (xx.x %)	xx (xx.x %)	xx (xx.x %)	xx (xx.x %)	xx (xx.x %)	xx (xx.x %)
SOC 1	All						
	PT 1						
	PT 2						
	.....						
SOC 2	All						
	PT 1						
	PT 2						
	.....						

**Note:** + CpG1018 1.5 mg (Adjuvant)

“xx” represent the value number.

“NE” represent the number of medical history events

**Table 13: Overall Number of Subjects at Least One Medical History by System Organ Class (SOC) and Preferred Term (PT)**

System Organ Class (SOC)	Preferred Term (PT)	All (N = 120)	COVIVAC				Placebo (N = 20)
			1 µg (N = 25)	3 µg (N = 25)	10 µg (N = 25)	1 µg + CpG (N = 25)	
All SOC	All PT	xx (xx.x %)	xx (xx.x %)	xx (xx.x %)	xx (xx.x %)	xx (xx.x %)	xx (xx.x %)
SOC 1	All						
	PT 1						
	PT 2						
	.....						
SOC 2	All						
	PT 1						
	PT 2						
	.....						

**Note:** + CpG1018 1.5 mg (Adjuvant)

“xx” represent the value number.

“N” represent the number of subject who has at least one medical history.

**Table 14: Number of Subjects at Least One Past Medical History by System Organ Class (SOC) and Preferred Term (PT)**

System Organ Class (SOC)	Preferred Term (PT)	All (N = 120)	COVIVAC				Placebo (N = 20)
			1 µg (N = 25)	3 µg (N = 25)	10 µg (N = 25)	1 µg + CpG (N = 25)	
All SOC	All PT	xx (xx.x %)	xx (xx.x %)	xx (xx.x %)	xx (xx.x %)	xx (xx.x %)	xx (xx.x %)
SOC 1	All						
	PT 1						
	PT 2						
	.....						
SOC 2	All						
	PT 1						
	PT 2						
	.....						

**Note:** + CpG1018 1.5 mg (Adjuvant)

“xx” represent the value number.

“N” represent the number of subject who has at least one medical history.

**Table 15: Number of Subjects at Least One Current Medical History by System Organ Class (SOC) and Preferred Term (PT)**

System Organ Class (SOC)	Preferred Term (PT)	All (N = 120)	COVIVAC				Placebo (N = 20)
			1 µg (N = 25)	3 µg (N = 25)	10 µg (N = 25)	1 µg + CpG (N = 25)	
All SOC	All PT	xx (xx.x %)	xx (xx.x %)	xx (xx.x %)	xx (xx.x %)	xx (xx.x %)	xx (xx.x %)
SOC 1	All						
	PT 1						
	PT 2						
	.....						
SOC 2	All						
	PT 1						
	PT 2						
	.....						

**Note:** + CpG1018 1.5 mg (Adjuvant)

“xx” represent the value number.

“N” represent the number of subject who has at least one medical history.

**Table 16: Number of Subjects Receiving at Least One Vaccination in the Past 1 Year**

Vaccine	All (N = 120)	COVIVAC				Placebo (N = 20)
		1 µg (N = 25)	3 µg (N = 25)	10 µg (N = 25)	1 µg + CpG (N = 25)	
.....	xx (xx.x %)	xx (xx.x %)	xx (xx.x %)	xx (xx.x %)	xx (xx.x %)	xx (xx.x %)
.....						
.....						

**Note:** + CpG1018 1.5 mg (Adjuvant)

“xx” represent the value number.

“N” represent the number of subject who has at least one medical history.

**Table 17: Summary of Visit Attendance and Sample Collection, Exposed Population**

Day	Study Visit							
	Screening	1 	8	29 	36	43	57	197
Completed visits								
1 µg (N = 25)	x (%)	x (%)	x (%)	x (%)	x (%)	x (%)	x (%)	x (%)
3 µg (N = 25)	x (%)	x (%)	x (%)	x (%)	x (%)	x (%)	x (%)	x (%)
10 µg (N = 25)	x (%)	x (%)	x (%)	x (%)	x (%)	x (%)	x (%)	x (%)
1 µg + CpG (N = 25)	x (%)	x (%)	x (%)	x (%)	x (%)	x (%)	x (%)	x (%)
Placebo (N = 20)	x (%)	x (%)	x (%)	x (%)	x (%)	x (%)	x (%)	x (%)
All (N= 120)	x (%)	x (%)	x (%)	x (%)	x (%)	x (%)	x (%)	x (%)
Functional humoral immune response by PNA								
1 µg (N = 25)		x (%)				x (%)		x (%)
3 µg (N = 25)		x (%)				x (%)		x (%)
10 µg (N = 25)		x (%)				x (%)		x (%)
1 µg + CpG (N = 25)		x (%)				x (%)		x (%)
Placebo (N = 20)		x (%)				x (%)		x (%)
All (N= 120)		x (%)				x (%)		x (%)
Anti-S IgG response by ELISA								
1 µg (N = 25)		x (%)				x (%)		x (%)
3 µg (N = 25)		x (%)				x (%)		x (%)
10 µg (N = 25)		x (%)				x (%)		x (%)
1 µg + CpG (N = 25)		x (%)				x (%)		x (%)
Placebo (N = 20)		x (%)				x (%)		x (%)
All (N= 120)		x (%)				x (%)		x (%)

**Note:** N = number of participants in the safety analysis population.

 Samples collected and assay results available.

 Vaccination day

Data are only expected at visits indicated by x (%).

**Table 18: Solicited Injection Site and Systemic Reactions Toxicity Grading Table- Protocol Appendix 1**

Reaction to Injectable Product	Mild (Grade 1)	Moderate (Grade 2)	Severe (Grade 3)	Potentially Life Threatening (Grade 4)
Pain/Tenderness	Does not interfere with activity	Some interference with activity OR Repeated use of non-narcotic pain reliever > 24 hours	Significant; prevents daily activity OR Any use of narcotic pain reliever	Emergency room (ER) visit or hospitalization
Erythemaa	2.5 – 5 cm	5.1 – 10 cm	> 10 cm and/or ulceration OR secondary infection OR phlebitis OR sterile abscess OR drainage	Necrosis or exfoliative dermatitis
Swelling/Indurationa	2.5 – 5 cm and does not interfere with activity	5.1 – 10 cm OR Interferes with activity	> 10 cm OR prevents daily activity and/or ulceration OR secondary infection OR phlebitis OR sterile abscess OR drainage	Necrosis
Temperature (oral)	38.0 – 38.4°C 100.4 – 101.1°F	38.5 – 38.9°C 101.2 – 102.0°F	39.0 – 40°C 102.1 – 104°F	> 40°C > 104°F
Headache	No interference with activity	Some interference with activity OR Repeated use of nonnarcotic pain reliever >24 hours	Significant; prevents daily activity OR Any use of narcotic pain reliever	ER visit or hospitalization
Fatigue/Malaise	No interference with activity	Some interference with activity	Significant; prevents daily activity	ER visit or hospitalization
Myalgia	No interference with activity	Some interference with activity	Significant; prevents daily activity	ER visit or hospitalization
Arthralgia	No interference with activity	Some interference with activity	Significant; prevents daily activity	ER visit or hospitalization
Nausea/Vomiting	No interference with activity	Some interference with activity	Prevents daily activity OR Requires outpatient IV hydration	ER visit or hospitalization for hypotensive shock

a For erythema and swelling/induration, longest diameter should be noted in centimeters. Swelling/induration should be evaluated and graded using the functional scale as well as the actual measurement.

The grading scales for local and systemic AEs have been derived from *Guidance for Industry, Toxicity Grading Scale for Healthy Adult and Adolescent Volunteers Enrolled in Preventive Vaccine Clinical Trials*, U.S. Department of Health and Human Services, FDA, CBER, September 2007 (<https://www.fda.gov/media/73679/download>) and the *Division of AIDS (DAIDS) Table for Grading the Severity of Adult and Pediatric Adverse Events* (Version 2.1, July 2017) from the US NIH (<https://rsc.niaid.nih.gov/sites/default/files/daidsgradingcorrectedv21.pdf>).

**Table 19: Vital Signs Toxicity Grading – Protocol Appendix 2**

Vital Signs a	Mild (Grade 1)	Moderate (Grade 2)	Severe (Grade 3)	Potentially Life Threatening (Grade 4)
Tachycardia – beats per minute	101 – 115	116 – 130	> 130	Hospitalization for arrhythmia
Bradycardia – beats per minuteb	50 – 54	45 – 49	< 45	ER visit or hospitalization for arrhythmia
Hypertension (systolic) – mm Hg	141 – 150	151 – 165	> 165	ER visit or hospitalization for malignant hypertension
Hypertension (diastolic) – mm Hg	91 – 99	100 – 105	> 105	ER visit or hospitalization for malignant hypertension
Hypotension (systolic) – mm Hg	85 – 89	80 – 84	< 80	ER visit or hospitalization for hypotensive shock
Respiratory Rate – breaths per minute	21 – 23	24 – 27	> 27	Intubation

a Subject should be at rest for all vital sign measurements.

b Grade 1 bradycardia or grade 1 tachypnea will not be considered an abnormality for this study, unless judged to be clinically significant by the PI in consultation with the Sponsor.

The grading scales for abnormal vital signs have been derived from *Guidance for Industry, Toxicity Grading Scale for Healthy Adult and Adolescent Volunteers Enrolled in Preventive Vaccine Clinical Trials*, U.S. Department of Health and Human Services, FDA, CBER, September 2007.

**Table 20: Serum Toxicity Grading – Protocol Appendix 3**

Serum	Mild (Grade 1)	Moderate (Grade 2)	Severe (Grade 3)	Potentially Life Threatening (Grade 4)
Creatinine (mg/dL)	1.1 – 1.3 x ULN	> 1.3 – 1.8 x ULN OR increase of > 0.3 above baseline	> 1.8 – < 3.5 x ULN OR increase of 1.5 – < 2.0 x above baseline	≥ 3.5 x ULN OR increase of > 2.0 x above baseline
Liver function tests – AST, ALT increased	1.25 – < 2.5 x ULN	2.5 – < 5.0 x ULN	5.0 – < 10.0 x ULN	≥ 10.0 x ULN
Total bilirubin	1.1 – < 1.6 x ULN	1.6 – < 2.6 x ULN	2.6 – < 5.0 x ULN	≥ 5.0 x ULN

Abbreviation: ULN = upper limit of normal range

Note: the laboratory values provided in this table serve as guidelines and are dependent upon institutional normal parameters.

The grading scales for laboratory abnormalities have been derived from *Guidance for Industry, Toxicity Grading Scale for Healthy Adult and Adolescent Volunteers Enrolled in Preventive Vaccine Clinical Trials*, U.S. Department of Health and Human Services, FDA, CBER, September 2007, and the *Division of AIDS (DAIDS) Table for Grading the Severity of Adult and Pediatric Adverse Events* (Version 2.1, July 2017) from the US NIH.

**Table 21: Hematology Toxicity Grading – Protocol Appendix 3**

Hematology	Mild (Grade 1)	Moderate (Grade 2)	Severe (Grade 3)	Potentially Life Threatening (Grade 4)
Hemoglobin [Female] (g/dL)	11.0 – 12.0	9.5 – 10.9	8.0 – 9.4	< 8.0
Hemoglobin [Male] (g/dL)	12.5 – 13.5	10.5 – 12.4	8.5 – 10.4	< 8.5
OR Hemoglobin, change from baseline value (g/dL)	1.0 – 1.5	1.6 – 2.0	2.1 – 5.0	> 5.0
WBC, increased (cell/mm  )	10,800 – 15,000	15,001 – 20,000	20,001 – 25,000	> 25,000
WBC, decreased (cell/mm  )	2,500 – 3,400	1,500 – 2,499	1,000 – 1,499	< 1,000
Platelets, decreased (cell/mm  )	100,000 – <125,000	50,000 – < 100,000	25,000 – < 50,000	< 25,000

Abbreviation: ULN = upper limit of normal range

Note: the laboratory values provided in this table serve as guidelines and are dependent upon institutional normal parameters.

The grading scales for laboratory abnormalities have been derived from *Guidance for Industry, Toxicity Grading Scale for Healthy Adult and Adolescent Volunteers Enrolled in Preventive Vaccine Clinical Trials*, U.S. Department of Health and Human Services, FDA, CBER, September 2007, and the *Division of AIDS (DAIDS) Table for Grading the Severity of Adult and Pediatric Adverse Events* (Version 2.1, July 2017) from the US NIH.

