## 8.6. Clinical Laboratory Evaluations

Screening viral serology assessments for Hepatitis B (HBsAg) and Hepatitis C (HCV Ab) will be described as categorical variables on a demographics table ([Table 28](#)).

Clinical safety laboratory values (serum hematology and chemistry) are collected at screening and 7 days post-vaccination for each dose. They will be summarized for the safety analysis population. Hematology and chemistry results evaluated at screening will be summarized as continuous variables by vaccine groups ([Table 24](#) through [Table 27](#)).

Screening and post-vaccination (Day 8 and Day 36) serum hematology and chemistry will be graded by severity. Grade 2 or higher were automatically considered as clinically significant and reported as AE, while Grade 1 abnormalities were subject to investigator opinion.

Continuous summaries of laboratory parameters (Hgb, WBC count, Plt, AST, ALT, total bilirubin, and creatinine) and the change from baseline will be computed by time point (including unscheduled visits, in chronological order) and treatment group, including mean, standard deviation, median, 1st and 3rd quartiles (IQR) and range, for all observations regardless of abnormality status (see [Table 60](#) through [Table 68](#)). Summaries will also be produced presenting the proportion of each severity grading using the number of subjects that provided a sample as denominator, as well as those considered clinically significant, using the maximum severity for a given subject, where relevant. A summary of safety laboratory abnormalities will be prepared by parameter, severity (by grade and any abnormality), and time point. Fisher's exact 2-tailed test will be used to test the differences in abnormality rates across all groups, by time point for scheduled visits, and overall.

Figures will be prepared for each laboratory parameter using boxplots to describe the distribution of values and changes from baseline across visits, by group, incorporating unique points and/or colors for abnormalities ([Figure 2](#) through [Figure 8](#)).

A listing of all lab results will be prepared, in addition to a listing only for abnormalities, and each will include the parameter, study day (Visit), value, units, change from baseline, LLN/ULN, and abnormality grade ([Listing 9A](#), [Listing 9B](#), Appendix 3).

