**Table 61: Hemoglobin Value at each Follow-up Visit Compared to Baseline (continued)**

Hemoglobin (g/dL)	All (N = 120)	COVIVAC				Placebo (N = 20)		
		1 µg (N = 25)	3 µg (N = 25)	10 µg (N = 25)	1 µg + CpG (N = 25)			
Change between Day 8 and Baseline								
Mean of % Difference (95% CI)								
Visit 4 (Day 36)								
n								
Mean (SD)								
Median (q1-q3)								
Min-Max								
*p-value =								
Normal								
Abnormal								
Mild								
Moderate								
Severe								
Potentially life threatening								
**p-value=								
Change between Day 36 and Baseline								
Mean of % Difference (95% CI)								

**Note:** + CpG1018 1.5 mg (Adjuvant)

\* P-value based on paired t test/ Wilcoxon signed-rank test

\*\* P-value based on Mc Nemar chi-square test, Normality of results (Normal/Abnormal) will be tested significant difference.

A significance test comparing a baseline (pre-vaccination) with a follow up measurement separately in vaccination group.

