**Severity grading**

Hemoglobin (g/dL)	Mild (Grade 1)	Moderate (Grade 2)	Severe (Grade 3)	Potentially Life Threatening (Grade 4)
Female	11.0 – 12.0	9.5 – 10.9	8.0 – 9.4	< 8.0
Male	12.5 – 13.5	10.5 – 12.4	8.5 – 10.4	< 8.5
Change from baseline value (g/dL)	1.0 – 1.5	1.6 – 2.0	2.1 – 5.0	> 5.0

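### Table 61 lets a follow-up haemoglobin be Abnormal by level or by change, but a baseline value by level only, which biases the within-group McNemar test towards new abnormality

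*SAP*

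**What the plan says.** - **Grading rule.** Table 21 (Appendix 1.A) gives level rows for women and for men ("Hemoglobin [Male] (g/dL")), in which lower values earn higher grades. It then adds "OR Hemoglobin, change from baseline value (g/dL"): Grade 1 is 1.0-1.5, Grade 2 is 1.6-2.0, Grade 3 is 2.1-5.0 and Grade 4 is above 5.0. No direction is given. In the same table the WBC rows are marked increased or decreased and the platelet row decreased.
- **Applied to Table 61.** The severity key under Table 61 repeats the level rows and "Change from baseline value (g/dL"). The shell shows Normal and Abnormal at baseline, Day 8 and Day 36, with Mild to Potentially life threatening listed under Abnormal.
- **Test.** The footnote reads "P-value based on Mc Nemar chi-square test, Normality of results (Normal/Abnormal) will be tested significant difference", and then "A significance test comparing a baseline (pre-vaccination) with a follow up measurement separately in vaccination group".
- **Visits graded.** Section 8.6: "Screening and post-vaccination (Day 8 and Day 36) serum hematology and chemistry will be graded by severity".
- **Consequence of a grade.** Section 8.6: "Grade 2 or higher were automatically considered as clinically significant and reported as AE". Grade 1 is left to the investigator.
- **Baseline.** The note closing Section 4.2.3 takes the last screening measurement as baseline.

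**The concern.** McNemar tests whether the proportion abnormal is the same at two times in the same people. That is a fair null only if abnormal means the same thing at both times. Here it does not. A baseline value has zero change from itself, so it can be Abnormal only by level, whereas a follow-up value can qualify by level or by change. Ordinary within-person and assay variation will push some subjects past 1.0 g/dL, and every such subject who was Normal at baseline counts as a new abnormality with no matching route in reverse.

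What is at stake is a set of within-arm p-values for a laboratory safety parameter, some of which may reflect the grading rule and not the product. Separately, because the change row has no direction, a rise of 1.6 g/dL is Grade 2 as written and so automatically an AE under Section 8.6.

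**Working it through.** The plan states no operating figure for this test, so there is nothing to reproduce.

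**Inputs from the SAP.** Level cut-offs for Grade 1 or worse: 13.5 g/dL or below (men), 12.0 or below (women). Change cut-off: 1.0 g/dL. Group sizes: 25 per active arm, 20 placebo (Section 4.4). Test: McNemar chi-square, within group.

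**Assumptions not in the SAP.** Half men; true means 14.8 (men) and 13.2 (women) g/dL; between-person SD 0.9; within-person plus assay SD 0.35-0.55; values rounded to 0.1; no true change; two-sided 5%; no continuity correction.

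**Step 1: chance of an apparent fall of 1.0 or more.** The difference of two readings has SD equal to s√2. After rounding, a fall of 1.0 or more means about 0.95 or more, so the probability is Φ(−0.95 / (s√2)):
- s = 0.35: Φ(−1.92) = 2.7%
- s = 0.45: Φ(−1.49) = 6.8%
- s = 0.55: Φ(−1.22) = 11.1%

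**Step 2: how few subjects are needed.** With c new and e resolved abnormalities, McNemar is (c − e)² / (c + e). For c = 4, e = 0 this is 16 / 4 = 4.00, p = 0.046. Four one-way moves in an arm of 25 are enough.

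**Step 3: simulated rejection with no true change, n = 25.**

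| Within-person SD | Level only, both visits | Level or fall | Level or change either way |
|---|---|---|---|
| 0.35 | 1.1% | 2.7% | 6.6% |
| 0.45 | 2.2% | 8.0% | 25.9% |
| 0.55 | 3.3% | 12.9% | 49.1% |

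Under level or fall, new against resolved abnormality is about 6-14% against 4-6% over this SD range. At 0.45 it is 9.8% against 4.9%, or 0.098 × 25 = 2.5 against 0.049 × 25 = 1.2 subjects per arm. Level-only grading gives 4.9% against 4.9%. At SD 0.40, rejection under level or fall is 5.2%.

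**Step 4: sensitivity to the assumptions.** With means 15.0 and 13.2 and between-person SD 1.0, level-or-fall rejection at n = 25 is 1.0%, 5.0%, 11.1%, 15.8% and 18.9% at within-person SD 0.3, 0.4, 0.5, 0.6 and 0.7. Level-only grading stays between 0.7% and 4.0%. The pattern is the same.

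**Step 5: reach.** WBC and platelets (Tables 62-63) use McNemar but have no change row. Creatinine has a change criterion, but the Table 65 footnote gives only Kruskal-Wallis. Haemoglobin is the only laboratory parameter affected.

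**The case against.** - **Abnormal might mean outside the reference range.** Section 8.3.1 speaks of values out of range, Section 8.6 mentions LLN/ULN, and Listings 9A and 9B carry a reference range. On that reading the asymmetry disappears. But the same sentence of Section 8.3.1 tabulates by toxicity grade, Table 61 places the grades under Abnormal, and its key includes the change row. Nothing excludes that row from the test.
- **The size is modest and rests on an assumed SD.** This stands. The SAP gives no within-person SD, and below about 0.4, with falls only, rejection in an arm of 25 stays at or under 5%. A reader might infer that the test will routinely report new abnormality when nothing has changed. The documents support a bias in that direction, not a significant result each time.
- **Larger figures depend on other readings.** At N = 120, falls only, rejection would be about 10-51%, but the footnote specifies testing separately by group, so that applies only if the All column is also tested. The 7-49% per arm needs the literal either-direction reading, which is less natural because the other haemoglobin rows grade low values.
- **Little hangs on the p-value.** This also stands. The primary endpoint in Section 3.2.1 concerns clinically significant measurements, Grade 1 is left to the investigator, and the interim report (Section 6.6.1) lists Tables 60 and 64 but not 61.
- **Level-only grading does not guarantee a valid test.** Correct. Eligibility (Sections 4.2.2 and 4.2.3) screens on laboratory results. In the extreme case where every low baseline is excluded, level-only McNemar at n = 25 rejects in 2-10% of null trials.

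**Conclusion.** The concern holds as a bias in the within-group comparison. Its direction follows from the SAP's own rules and needs no outside figure: the change row can act only after baseline, so with no true change new abnormality is expected to exceed resolved abnormality, in placebo as in the vaccine arms. Its size, about 3-13% rejection per arm of 25 against about 1-3% with level-only grading, depends on the assumed SD of 0.35-0.55 g/dL and on reading the change row as a fall.

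A reader might go further and infer that Table 61 would produce a vaccine-related signal or distort formulation selection. The documents do not support that. Placebo carries the same bias, the between-group Fisher test in Section 8.6 is not biased between arms by it, and no stated selection decision uses this p-value.

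The missing direction is a separate gap in the wording and stands without any simulation. The change should be made, but it is a correction to one table and not a threat to the trial's conclusions.

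**What to change.** 1. In Table 61, define Normal/Abnormal for the McNemar comparison by the absolute level criterion alone at baseline, Day 8 and Day 36.
2. Report change-from-baseline grades in a separate row for each arm, including placebo, with no test against baseline.
3. State the direction of the change row in Table 21 and in the Table 61 key, reconciled with the protocol appendix from which the scale is taken.
4. Add a note to Table 61 that screening on laboratory results can deplete abnormal baselines, so the within-arm p-value is descriptive and should be read against placebo.

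The cost is shell and footnote edits. No new data are needed and no clinical threshold changes.
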